- Compare changes in lip color, texture and volume before and after filler with non-invasive imaging, including digital photography, OCT and three-dimensional imaging
- To assess the tolerability of lip filler by evaluating pain level from lip filler treatment at initial insertion and overall procedural pain
- To evaluate how oxytocin levels change during and after an aesthetic procedure.
- To assess lip color change after the procedure.
- To evaluate patient satisfaction related to the procedure.

IV. SUBJECT SELECTION

Subjects will be screened to determine if they meet all the eligibility criteria specified below. We will recruit and screen up to 50 subjects with the goal of 40 subjects enroll and complete the study (20 per study arm).

a. Inclusion Criteria

1. Subjects must be able and willing to provide written informed consent and comply with the requirements of the study protocol;
2. In good general health, based on answers provided during the screening visit;
3. Subjects must be able to read and understand English;
4. Female subjects;
5. Aged 21-30 years and Post menopausal women;
6. Skin Types (Fitzpatrick Skin Phototypes I-VI);

* Smoking history is self-report.

7. Have very thin to moderately thick lips (Lip Fullness Grading Scale [LFGS] scores 0–2).

b. Exclusion Criteria

1. Participation in another investigational drug or device clinical trial in the past 30 days;
2. Are pregnant or lactating;
3. Intake of hormone replacement therapy (HRT) in the past 6 months;
4. Have a history of drug or alcohol abuse or have reported habitual alcohol intake greater than 2 standard drinks per day [e.g., 2 beers, 2 glasses of wine, or 2 mixed drinks];
5. Presence of eczema, psoriasis, or any other skin disease on the lips or perioral skin;
6. Have birth marks, tattoos, scars, or any other disfiguration of the skin in the skin area of interest;
7. Use of any anti-aging skin care products containing retinoic acid, retinol, or other retinoids (e.g. tazarotene, adapalene) or estrogen on the skin area of interest in the past 6 months;
8. Use of any prescription topical medication, such as corticosteroids or hydroquinone on the skin area of interest in the past 6 months;
9. Have a history of photodynamic therapy treatment or any skin rejuvenation procedure on the skin area of interest;
10. History of blood-clotting abnormality;
11. History of keloid formation or hypertrophic scarring;

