- Three-dimensional imaging using the Cherry Imaging system (before and after the procedure)
- Digital photography of the lips and perioral area

Filler treatment of the lips with Restylane Kysse (if the subject has completely inverted lips the lip filler procedure will be optional and only imaging will be collected in visit 1)

- Lip volume assessment with Lip Fullness Grading Scale
- Subjects will be instructed how to report a pain score for first needle insertion and overall procedural pain. A visual 10 point pain scale will be used.

Wong-Baker FACES® Pain Rating Scale

©1983 Wong-Baker FACES Foundation. www.WongBakerFACES.org
Used with permission. Originally published in *Whaley & Wong's Nursing Care of Infants and Children*. ©Elsevier Inc.

- Intravenous access will be placed to facilitate four blood draws to analyze serum oxytocin levels, all of which will occur on Visit 1 as follow: after photography and OCT, and before the filler procedure starts, immediately after the filler procedure, after the “mirror reveal” (when we show the lips to the subject using a mirror) minutes and 30- 35 minutes after the filler procedure has been concluded.
- The questionnaires: “FACE-Q™ – satisfaction with outcome” and other questions will be applied right after the procedure to evaluate subject’s satisfaction and about lip color and shape changes.
- Documentation of Adverse Events
- Video recording (15-30 seconds-video) from subjects’ face and lips after the lip filler procedure. The video recording is optional.
- Upon completion of all treatments, the subject will be provided with aftercare instructions, remuneration and parking voucher if needed

Follow-up Call (3-7 days after Visit 1, 30 minutes)

Study staff will call the subject 3-7 days after Visit 1 to check-in and inquire about any post-procedure pain or any side effects. If there are any negative side effects from treatment, they will be evaluated and treated in accordance with standard medical procedures.

Visit 2 (2 weeks after Visit 1, 1 hour)

Subjects will be asked to return 2 weeks after Visit 1. Visit 2 is expected to last up to 1 hour. The following procedures and evaluations will be performed:

- Three-dimensional imaging using the Cherry Imaging system
- OCT imaging for microvasculature
- Digital photography of the lips and perioral area
- Lip volume assessment with Lip Fullness Grading Scale (LFGS)
- Documentation of adverse events

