A DSLR camera will be used to take images of the lips and perioral area before the dermal filler procedure takes place during visit 1 and then at the second study visit. Subjects will be asked to stand with limited facial expression so that consistent, photographic images can be obtained.

Video Recording

Study's encrypted Iphone 12 (no chip inside, used only for the study) will be used by study staff (investigator or research coordinators) to take a video recording from the subjects' face/ reaction during the "mirror reveal". From 15 to 30 seconds of video recording will be taken from subject's face after a mirror is used to show them their "new lips". This will happen after the dermal filler procedure takes place during visit 1. This video will be optional and subjects will express if they allow this video recording or not in the consent form. Subject's reaction after the "mirror reveal" will be correlated to Oxytocin levels.

Restylane Kysse Lip Filler Treatment

After the OCT imaging, Cherry Imaging and digital photography, Restylane Kysse lip filler will be injected into the submucosal layer of the lips and subcutaneous layer of the perioral area. This hyaluronic acid filler formulation contains local anesthetic lidocaine so no topical anesthetic will be applied. The subject will be positioned in a seated position and the treatment area will be cleaned prior to injection. One syringe with 1mL will be injected to lips and perioral area in accordance with standard aesthetic lip filler practices. We aim to inject the full amount of one syringe, but upon the investigators discretion we may inject +/- 0.25mL as needed. The area will then be gently massaged with Vaseline to ensure the dermal filler gel is distributed evenly [9]. The subject will experience sharp pain and mild pressure from initial injection, which will subside with subsequent insertions as the lidocaine numbing takes effect. Standard of care for aesthetic lip filler treatment will be followed.

Blood Draw

Four blood draws to analyze serum oxytocin levels, all of which will occur on Visit 1 as follow:

- After photography and OCT, and before the filler procedure starts, an intravenous access will be placed and approximately 3 cc of blood will be drawn into EDTA tubes containing Aprotinin supplied by the Brigham Research Core lab.

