- Immediately after the filler procedure, approximately 3 cc of blood will be drawn into EDTA tubes containing Aprotinin supplied by the Brigham Research Core lab.
- after the after the "mirror reveal" (when we show the lips to the subject using a mirror approximately 3 cc of blood will be drawn into EDTA tubes containing Aprotinin supplied by the Brigham Research Core lab.

- 30-35 minutes after the filler procedure has been concluded, a final approximate of 3 cc of blood will be drawn into EDTA tubes containing Aprotinin supplied by the Brigham Research Core lab.

Each sample will be allowed to clot for 30-60 minutes at room temperature to prepare serum, then centrifuged at 1600 x g for 15 minutes at 4°C by study staff, and the serum will be transferred to plastic tubes.

The samples will be placed on dry ice and hand-delivered by the research staff to the Brigham Research Core lab or stored at -80 degrees freezer located at the MGH Navy Yard in the [name] lab when immediate delivery is not possible.

The Brigham Research Core lab will process the ELISA assay to evaluate oxytocin levels.

e. Data to be collected and when data is collected

Study data will be collected during each study visit. Study data to be collected includes OCT imaging (various images as described above, visit 1 and 2), digital photography and Cherry Imaging of the lips and perioral area (visit 1 and 2), visual assessment of treated area (visit 2), video recording (optional) from subject's reaction after the mirror reveal, Lip volume assessment with Lip Fullness Grading Scale (screening visit, visit 1 and 2), pain assessment of initial injection and overall procedure (visit 1), blood samples (visit 1) and satisfaction questionnaire answers (visit 1 and 2). Medical history and medications will be documented at visit 1. There are no other biological data or health information to be collected in this study.

Information about side effects in the treatment area or any adverse events will be collected during the follow-up call and visits.

f. Remuneration

Subjects will be paid \$50 for completing all imaging activities and filler treatment during visit 1, and \$100 for completing visit 2. The total remuneration amount is \$150 upon completing the study. We will provide a parking voucher at MGH main campus for each visit upon request.

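### The oxytocin draw-to-spin time may be anything from 30 to 60 minutes and is not listed for recording, so handling can differ between a woman's own draws (minor, cheap to fix)

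*Combined protocol and SAP*

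**What the plan says.** Section III includes the aim "To evaluate how oxytocin levels change during and after an aesthetic procedure". Section VI.a (Visit 1) provides for it: "Intravenous access will be placed to facilitate four blood draws to analyze serum oxytocin levels". The draws are:

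- Draw 1, baseline: "After photography and OCT, and before the filler procedure starts, an intravenous access will be placed", and the first sample is taken then.
- Draw 2: "Immediately after the filler procedure, approximately 3 cc of blood will be drawn into EDTA tubes containing Aprotinin".
- Draw 3: after the mirror reveal. Section VI.a gives no number of minutes for it; the text reads "when we show the lips to the subject using a mirror) minutes and 30- 35 minutes after the filler procedure has been concluded".
- Draw 4: "30-35 minutes after the filler procedure has been concluded, a final approximate of 3 cc of blood will be drawn".

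For every draw, section VI.d (Blood Draw) continues: "Each sample will be allowed to clot for 30-60 minutes at room temperature to prepare serum". Study staff next run a cooled spin (4°C) lasting 15 minutes. The section does not fix a time within the window or say whether tubes are spun singly or together. The data list in VI.e names blood samples at visit 1, and the list in XII.a adds laboratory results. Neither mentions draw or spin times. Section VII.c is descriptive and does not mention oxytocin.

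**The concern.** The four values are read against each other within one woman, so anything in the handling that changes with draw order is mixed up with the change being measured. Standing time can do this. The earlier tubes in a shared spin necessarily wait longer, and if oxytocin is lost while waiting, the earlier values are lowered relative to the later ones. A shift in the same direction in every subject would not average out with more subjects. There is no untreated oxytocin group to show a handling trend, and without recorded times the trend could be neither detected nor adjusted for later.

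If standing times vary without a pattern, the harm is milder. Noise is added to each woman's change, which weakens the intended links with satisfaction (section II) and with the reaction to the reveal (VI.d, Video Recording).

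**Working it through.** **Inputs from the documents.** Standing window 30 to 60 minutes and spin 15 minutes (VI.d). Draw 4 is 30 to 35 minutes after the procedure ends (VI.d). Draw 2 is immediately after the procedure, taken here as time 0. Visit 1 lasts 1.5 hours (VI.a).

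**Not given, so assumed.** Filler session 15 to 20 minutes and reveal 5 to 10 minutes later, so draw 1 precedes draw 3 by 20 to 30 minutes. Loss on standing, k, between 0 and 1% per minute. The plan states no figure on this point, so there is none to reproduce.

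**Step 1: largest difference allowed.** 60 − 30 = 30 minutes, in either direction.

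**Step 2: which draws can share a spin.** The later tube must stand at least 30 minutes, so the earlier one stands gap + 30, which must not exceed 60. The gap must therefore be 30 minutes or less.

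| Draws | Gap | Shared spin within the window? |
|---|---|---|
| 1 and 2 | filler duration, not given | yes if 30 min or less (at 15 min, draw 1 stands 45 and draw 2 stands 30) |
| 1 to 3 | not given | yes if 30 min or less |
| 2 and 4 | 30–35 min | only at exactly 30 min; at 35, draw 2 would stand 65 |
| 1 and 4 | filler duration + 30–35 min | never; draw 1 would stand more than 60 |

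Is 20 to 30 minutes from draw 1 to draw 3 plausible? The visit leaves 90 − 35 = 55 to 90 − 30 = 60 minutes before the end of filler for eligibility review, imaging, venous access and the injection. The assumed span fits that, but the documents do not state it.

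**Step 3: size of an artefact.** If the earlier tube stands d minutes longer, the apparent rise is exp(k × d) − 1.

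| Assumed loss per minute | d = 30 | d = 20 | d = 15 |
|---|---|---|---|
| 0 | 0% | 0% | 0% |
| 0.1% | 3.0% | 2.0% | 1.5% |
| 0.25% | 7.8% | 5.1% | 3.8% |
| 0.5% | 16.2% | 10.5% | 7.8% |
| 1% | 35.0% | 22.1% | 16.2% |

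The 20- and 30-minute columns bracket draw 1 against draw 3 in a shared spin. Draw 1 against draw 2 would differ by 15 to 20 minutes. The top rate is a half-life of ln 2 / 0.01, about 69 minutes; the lowest non-zero rate is ln 2 / 0.001, about 693 minutes.

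**Step 4: after a fix.** With identical standing times, a common proportional loss cancels in within-person ratios. With a tolerance of plus or minus 5 minutes, the largest difference is 10 minutes, and the same formula gives 1.0%, 2.5%, 5.1% and 10.5% at the four non-zero rates.

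**The case against.** The strongest reply is that the bias needs three unstated things together. Staff must batch draws 1 to 3; those draws must fall within 30 minutes, with no slack at the full 30; and oxytocin must be lost at a material rate in these tubes. The window equally permits equal or reversed standing times. No passage says that oxytocin is lost on standing. The protocol expressly allows room temperature at this step, and the tubes contain aprotinin, a protease inhibitor that may reduce loss. The cold spin, dry ice and −80 storage come afterwards. The assay follows a kit (VII.b) whose handling instructions are not in the documents. All of this stands, and it limits the point to a possibility of unknown size.

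It also rules out three stronger readings that a reader might infer:

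- That the 30-minute spread matches the gap between draws. Only the draw 2 to draw 4 gap can be derived (30 to 35 minutes); the others have no minutes.
- That an artefact would run through the whole series. Draws 1 and 4 can never share a spin within the window.
- That a false rise would mimic the effect sought. The aim in section III has no direction, and no passage hypothesises a rise.

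Finally, a proportional shift common to all subjects would leave between-subject correlations with satisfaction or reaction essentially unchanged; only irregular standing times would weaken them.

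What the reply does not answer is that nothing in the text prevents standing time from following draw order, and nothing listed for recording would show whether it did.

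**Conclusion.** The point holds as a minor, inexpensive improvement. The draw-to-spin time is not fixed, not listed for recording and not balanced across draws, so it can differ by up to 30 minutes between one woman's samples. The effect is noise if the times vary irregularly, and an apparent rise from baseline if draws 1 to 3 share a spin and oxytocin is lost on standing. The size is unknown: about 0% to 35% at the full 30 minutes for assumed losses of 0 to 1% per minute, and 0% to 22% for draw 1 against draw 2 at an assumed 15 to 20 minutes. The documents do not support saying that a bias will occur or that every subject will be affected.

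A firmer inconsistency lies in the same section. EDTA is an anticoagulant, yet blood drawn into EDTA tubes is to clot and yield serum. Until that is reconciled, the clotting window has no settled meaning. A consistent draw-to-spin time is needed whichever sample type is intended.

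**What to change.** 1. Reconcile the EDTA tubes with the instruction to clot and prepare serum (VI.a and VI.d), and state the sample type.
2. Replace the range with one target draw-to-spin time and a narrow tolerance, for example plus or minus 5 minutes, for all four draws. If the 30 to 60 minute limits are kept, the target must lie between 35 and 55 minutes so that the tolerance stays inside them.
3. Allow a shared spin only when every tube in it is within tolerance. A rule that each draw must have its own spin at exactly the same interval would not work on one centrifuge: draws 2 and 3 taken 5 to 10 minutes apart would collide with a 15-minute spin. With plus or minus 5 minutes, two draws can share a spin if they are 10 minutes apart or less. They can be spun separately if they are at least 5 minutes apart: the first starts 5 minutes early, the second 5 minutes late, and loading time is ignored.
4. Record draw and spin times on the case report form and add them to VI.e.

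The cost is a short change to VI.d, two time fields per draw, and about three or four short spins per subject instead of about two. No extra blood or equipment is needed.

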We will be using an approved, outside vendor (Forte Research) to make these payments via a reloadable credit card-based system, called Forte Payments. This secure system is similar to a gift card or credit card.

If subjects are paid by this system, they will be given a Forte Payments Via card (which is just like a debit card) when subjects enroll in the study. Once the card is activated, the study team will add a payment after each paid visit completed by the subjects. The payment should be available within one (1) business day. Research staff will not know where subjects spend the money. You may use the card anywhere Visa cards are accepted, such as at a grocery store.

We will need to collect subjects' Social Security number in order to make these payments, and it will be shared securely with the company that runs the card-based system. Payments like this are considered taxable income. If subjects receive more than \$600, the payment will be reported to the IRS as income by the hospital.

VII. BIOSTATISTICAL ANALYSIS

a. Study Variables

Aesthetic Procedure Improvement Analysis

The Global Aesthetic Improvement Scale (GAIS) is a five-point scale used to assess effectiveness of aesthetic procedures comparing pre-treatment and post treatment. This scale ranges from 1 = exceptional improvement, 2 = very improved patient, 3 = improved patient, 4 = unaltered patient, 5 = worsened patient [11, 13].

Degree	Description
1	Exceptional improvement
2	Very improved patient
3	Improved patient
4	Unaltered patient
5	Worsened patient

Lip Volume Analysis

Lip Fullness Grading Scale (LFGS) will be used to assess the lip volume change from pretreatment compared to post treatment. This photonumeric rating scale ranges from 0 = very thin; 1 = thin; 2 = moderately thick; 3 = thick; and 4 = full. Improvement of lip volume is defined as ≥ 1 increase at post-treatment compared to pretreatment [11, 14].

Pain Scoring Analysis

The Wong-Baker FACES Pain Rating Scale will be used to score subject pain from the first insertion of dermal filler and the overall pain from the procedure.

Wong-Baker FACES® Pain Rating Scale

©1983 Wong-Baker FACES Foundation. www.WongBakerFACES.org
Used with permission. Originally published in *Whaley & Wong's Nursing Care of Infants and Children*. ©Elsevier Inc.

b. Study Analyses

OCT analysis

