OCT imaging is performed using the commercially available spectral-domain OCT scanner TELESTO II (Thorlabs Inc., Newton, New Jersey). It operates at a central

wavelength of 1,300 nm with a maximum output power of less than 10 mW. Using a lens with an optical lateral resolution of 13 μm (LSM03, Thorlabs Inc.), we acquire images with an oversampling factor of 2 \times leading to voxel sizes of $6.5 \times 6.5 \times 3.5 \mu\text{m}^3$ and a field-of-view (FOV) of $6 \times 6 \times 3.5 \text{ mm}^3$ (length \times width \times depth), acquired at an A-Scan rate of 76 kHz.

The imaging data is further processed and analyzed by custom made software tools implemented in MATLAB 2016b (MathWorks Inc). All OCT image data files will be labeled with the study subject number assigned to each subject upon consent. No identifying information will be used in labeling the image data files and the files will be stored on Partners OneDrive.

With angiographic image post processing, the capillary layer, typically in between 70 – 400 μm depth in skin, is displayed and converted to 2-dimensional images as maximum intensity projections. These 2-dimensional images are further segmented by an automatic, customized software and quantitative metrics such as vessel area, vessel length, vascular network complexity (fractal dimension) and vessel curvature are assessed. These characteristics of the capillary network are further used for inter- and intra-cohort investigations.

Cherry Imaging Photography Analysis

The Cherry Imaging analysis software contains distinct algorithms that process the generated three-dimensional images to calculate volume in cubic centimeters, precise color using saturation and hue, roughness detecting local variations in height/depth, and a ruler function that measures the distance between two distinct points. These will all be employed to analyze photos of lips, lip redness, roughness and volume.

DSLR Camera Photography Analysis

Standard photographs will be blindly reviewed by a physician and assessed using the Lip Fullness Grading Scale and Global Aesthetic Improvement Scale.

Video Recording

Videos will be blindly reviewed by a physician and assessed using the following grading scale (this grading scale is based on the model of answers that are given to subjects in the questionnaire):

Very satisfied	Somewhat satisfied	Somewhat dissatisfied	Very dissatisfied
----------------	--------------------	-----------------------	-------------------

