There is a potential risk of loss of privacy. We will protect privacy by labeling samples, information, and data files only with a study subject number code, and keeping the key to the code in a password protected database.

IX. POTENTIAL BENEFITS

a. Potential Benefits to Subjects

Subjects who participate in this study will receive Restylane Kysse dermal filler treatment of the lips, which may improve the appearance of their lips.

b. Potential Benefits to Society

Information gathered from this study may improve the understanding of the pathological alteration of intrinsic aging to lip microvasculature and changes in color, roughness and/or appearance of lips before and after a lip filler procedure. This study may also aid in understanding pain tolerance with the lip filler procedure to improve pain management techniques in the future as needed.

X. MONITORING AND QUALITY ASSURANCE

a. Independent monitoring of source data

Experienced study personnel (study monitor) who are not assigned to complete procedures of this study will conduct monitoring after the first subject is enrolled and periodically thereafter. The monitor will be responsible for confirming the completion and correctness of the study procedures as well as record collection and keeping.

b. Safety monitoring

Prior to enrollment, subjects will be screened for eligibility; at which time a complete medical history, including a baseline assessment of the subject's lips will be done. Evaluations will be ongoing throughout the study to detect adverse events and changes in existing medical conditions.

At any time after enrollment, a subject may be discontinued. Reasons for discontinuation of a subject from the study will include, but may not be limited to, the following:

1. Subject is found to be intolerant to a required study procedure at any time point.
2. Subject is noncompliant with protocol restrictions and requirements.
3. Subject develops an intercurrent illness that would, in the judgment of the investigator, affect assessments of clinical status to a significant degree.
4. Subject becomes pregnant while participating in the study.
5. Subject enrolls in another investigational study.
6. Subject requests to withdraw from the study.
7. The study staff decides to suspend or terminate the study.

If possible, a final set of assessments will be performed on all subjects who end their participation prior to study completion.

c. Outcomes monitoring

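### The photo review is called blind without saying what is masked; GAIS as defined requires the rater to know which photo is post-treatment, so it may lean towards improvement

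*Combined protocol and SAP*

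**What the plan says.** All references are to the combined protocol and SAP.

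- **VII.b, DSLR Camera Photography Analysis.** One sentence describes the review: "Standard photographs will be blindly reviewed by a physician and assessed using the Lip Fullness Grading Scale and Global Aesthetic Improvement Scale". Nothing is said about what is masked, how photos are ordered or presented, or whether the reviewing physician also treats subjects.
- **VII.a, Aesthetic Procedure Improvement Analysis.** GAIS is a "five-point scale used to assess effectiveness of aesthetic procedures comparing pre-treatment and post treatment", with grades "1 = exceptional improvement, 2 = very improved patient, 3 = improved patient, 4 = unaltered patient, 5 = worsened patient".
- **VII.a, Lip Volume Analysis.** LFGS runs from 0 to 4 and change is derived afterwards: "Improvement of lip volume is defined as ≥ 1 increase at post-treatment compared to pretreatment".
- **VI.d, Digital Photography.** Photos are taken "before the dermal filler procedure takes place during visit 1 and then at the second study visit", so there are two time points.
- **IV.** The target is 40 completers, 20 per arm. Section I shows that the arms are age groups.
- **IX.a.** "Subjects who participate in this study will receive Restylane Kysse dermal filler treatment of the lips". Section VI.a makes one exception: "if the subject has completely inverted lips the lip filler procedure will be optional and only imaging will be collected in visit 1".
- **VII.c.** The analysis is descriptive, pre- against post-treatment.

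**The concern.** Calling a review blind tells the reader that the rater's expectations were kept out of the score. The GAIS definition does not allow that for time point. Someone who grades a pair as improved or worsened has to know which photo is the later one, and in this study the later photo is, with one exception, the treated one.

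The analysis is descriptive and has no comparator, so the proportion rated improved is itself the result. Nothing in the design would show how much of that proportion came from expectation. LFGS is read in the same review. It does not have the same built-in difficulty, but the plan does not commit to masking it.

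**Working it through.** The plan states no figure to reproduce here: no rater error, power or expected response. The check sets the definitions side by side and adds what arithmetic the documents allow.

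**1. What each scale needs from the rater**

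| Scale | What is graded | Must the rater know the time order? |
|---|---|---|
| GAIS (VII.a) | A pair, from improvement to worsening | Yes, as defined |
| LFGS (VII.a) | One photo, 0 to 4; change computed later | No |

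**2. What the blinding could refer to**

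- *Treatment assignment:* there is none to mask. The arms are age groups and filler is planned for all, apart from the exception in VI.a.
- *Identity:* XII.a has eyes and tattoos blacked out. This does not hide the visit.
- *Age group:* possible in principle, though age may show in perioral photos. It would not remove an expectation that the later photo looks better.
- *Visit:* the one form of masking that would address expectation. It is feasible for LFGS and not for GAIS as defined. The plan does not state it for either.

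**3. Whether another measurement would reveal a lean**

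The Cherry software (VII.b) calculates volume, colour and roughness. That is a partial objective check on LFGS. It does not measure overall aesthetic improvement, and no other source of GAIS ratings is described. LFGS is also recorded at the visits (VI.a, Appendix A), where the time point is known, so the photo review is the only place where LFGS can be masked.

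**4. What can be said about size**

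- Pairs: 2 × 20 = 40, if every completer has both photos.
- One pair moved from unchanged to improved: 1/40 = 2.5 percentage points overall, and 1/20 = 5 points within an age group. This is a unit of sensitivity, not an estimate of bias.
- An estimate would need a rater SD and an expectation shift m, and the documents give neither. In a simple model with no true change, the share rated improved is P(N(m, SD) > 0.5) = Φ((m − 0.5)/SD). At m = 0.5 this is Φ(0) = 50% for every SD. The output only returns the assumed input, so no such figure is used as evidence here.

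**5. Whether hidden-order ratings can be turned into GAIS**

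Three of the five grades are improvement (3/5 = 60%) and one is worsening (1/5 = 20%). A hidden-order score therefore cannot simply be flipped: grades 1 and 2 have no mirror image on the worse side. A collapsing rule is needed, and one is given under the fix. The asymmetry also matters for the summary. If Visit 2 and Visit 1 are each preferred equally often by two steps, the converted grades are 2 and 5, with mean (2 + 5)/2 = 3.5, which is on the improved side of 4 although the preferences balance. The share of pairs preferring each visit does not have this defect.

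**The case against.** The strongest reply is that the plan does not say photos are shown in known order. A team could hide the order, have the physician choose and grade, and unmask later, and the one sentence in VII.b does not forbid it. That is fair as far as it goes. However, the scale handed to the reviewer is the directional one in VII.a, and no hidden order or conversion step is described. As written, the rating needs the order.

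Several limits on the point stand:

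- A reader might infer that the whole photo review cannot be blind. The documents do not support that: LFGS can be graded with the visit hidden, and the fault there is silence.
- A reader might infer that every subject is treated. Filler is optional for completely inverted lips, and VI.a does not make clear whether such subjects have Visit 2 photos. This does not create a comparator arm.
- GAIS appears in none of the objectives or aims (I, III), no primary outcome is named, and lip volume, colour and roughness also have software measurements. The consequence is limited to the physician-rated results.
- Hiding the order is not complete protection. Added fullness is the intended effect, and VIII.b lists swelling and bruising as very common, so a reviewer may recognise the treated photo.

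**Conclusion.** The point holds in this form. VII.b claims a blind review without defining it. GAIS as defined in VII.a cannot be masked to time point, and no treatment assignment exists to mask in its place, so the claim gives the GAIS rating no protection against expectation. LFGS can be masked to visit, but the plan does not commit to it.

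The rating *may* lean towards improvement. A reader might go further and say that it will, or attach a percentage. The documents support neither: the direction is plausible, the size unknown. The conclusion rests on reading GAIS as VII.a defines it and on the absence of any untreated, sham or comparator-treatment arm. It does not depend on any assumed rater error. It is worth acting on because the proportion improved is the reported result and the remedy uses the same photos.

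**What to change.** Replace the sentence in VII.b with a short paragraph:

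1. **LFGS first.** Grade single, date-stripped photos shuffled across subjects and visits. Compute change after unmasking.
2. **GAIS second.** Show each subject's pair in random order with the visit hidden. Record which photo looks better, or no difference, and by how many steps. Convert after unmasking by a rule fixed in advance:
   - Visit 2 better by 1, 2 or 3 steps: grade 3, 2 or 1
   - no difference: grade 4
   - Visit 1 better by any amount: grade 5
3. **Report** the share of pairs in which Visit 2 was chosen as better, with the Visit 1 and no-difference counts beside it.
4. **Otherwise**, keep GAIS as it is and report it as not masked to time point.

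The paragraph should also say whether the reviewing physician took part in treatment, which the plan leaves open.

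Cost: one paragraph and a random order list for about 40 pairs, with the same photos and the same reviewer. Downsides: GAIS becomes a score derived after unmasking, and visible treatment effects may still give the visit away. The masking reduces expectation bias without removing it, and the report should say so.
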